	
assessed quantitatively by Duplex ultrasonography (DUS); OR, (2) for BTK lesions: freedom from occlusion (100% stenosis by DUS) combined with freedom from CD-TLR, at 6, 12, and 24 months.
 
4. Clinical outcomes, defined as change in ankle brachial index (ABI or TBI if needed), walking impairment questionnaire (WIQ), and Rutherford category at 6, 12, and 24, months, compared to baseline
 
Exploratory endpoint(s):
 
1. Intravascular ultrasound assessment pre- and post-Auryon and correlation with angiographic findings (e.g. lesion length, MLA -minimal lumen area gain, calcium severity and removal, etc.). This endpoint will be analyzed only for cases that used IVUS as a routine practice in the index procedure.

STUDY POPULATION:	
Patients with infra-inguinal PAD undergoing atherectomy with the AURYON Atherectomy System.
 
Inclusion Criteria A potential subject will be included in the study if he/she meets all the following inclusion criteria:
 
 1. Subject is ≥ 18 years old. 2. Subject is a candidate for atherectomy for infra-inguinal peripheral artery disease. 3. Documented symptomatic atherosclerotic peripheral artery disease with claudication or critical limb ischemia (CLI) (Rutherford Classification 2-5). 4. Subject is capable and willing to comply with the scheduled follow up 5. Subject is able and willing to sign a written Informed Consent Form (ICF). 
Exclusion Criteria A potential subject will be excluded from the study if he/she meets any of the following exclusion criteria:
 
 1. Target lesion is in an arterial bypass. 2. Planned use of another atherectomy device in the same procedure 3. Co-morbid condition(s) with less than 1yr anticipated survival that could limit the subject's ability to participate in the trial or to comply with follow-up requirements or impact the scientific integrity of the study.

	4. Participating in another study on an interventional non-cleared device, that could impact the study results

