DESCRIPTION OF SITES/FACILITIES ENROLLING PARTICIPANTS:	
This study will be conducted at sites where eligible PAD patients are routinely treated with atherectomy by AURYON Atherectomy System.
 
Total enrollment of approximately 100 subjects at approximately 10 sites in the US.
 
To reduce bias by sites, each site may enroll up to 15 eligible subjects whom have successfully completed their index atherectomy treatment with the AURYON system and with analyzable imaging for the primary efficacy analysis.

DESCRIPTION OF STUDY PROCEDURE:	Atherectomy by the AURYON system, of infra-inguinal stenoses, occlusions or in-stent restenosis (ISR).
STUDY DURATION:	The study duration is expected to be two and a half (2.5) years: 6 months to enroll and two (2) years to follow up all subjects.
PARTICIPANT DURATION:	Two (2) years
PRIMARY ANALYSIS PLAN:	
As this is a pilot registry study, no formal hypotheses are defined; rather statistical analyses will be descriptive in nature and will serve to provide estimates of the primary and secondary study endpoints.
 
Also, no formal sample size calculation was performed. The number of enrolled subjects will allow for sufficient safety monitoring and evaluation of the safety and efficacy endpoints and will provide point estimates for the large-scale registry.
 
Analysis sets:
 
Intent-to-treat (ITT) population: The intent-to-treat (ITT) population will consist of all subjects who signed the informed consent form and underwent procedure with an attempt of using the AURYON system.
 
Modified Intent-to-treat (mITT) population: The modified Intent-to-treat (mITT) population will consist of all ITT subjects who underwent atherectomy using the AURYON system for at least one lesion.
 
Per-protocol (PP) population

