	
The per-protocol (PP) population will consist of all mITT subjects for whom the AURYON catheter fully crossed at least one target lesion.
 
If a subject does not undergo complete procedure, either due to early or intraoperative non-eligibility of inclusion/exclusion criteria or due to missing evidence of significant arterial disease ($\geq 50\%$) by fluoroscopy angiogram in the index procedure, the subject will be considered as a screen failure. Screen failures will not be included into ITT population and will not be followed or part of the analysis.
 
If a subject undergoes an atherectomy attempt but the AURYON system could not be successfully used in any target lesion, the subject will be included into ITT population but excluded from mITT and PP populations. That subject will not be followed-up after discharge.
 
If a subject undergoes atherectomy using the AURYON system but the AURYON catheter cannot fully cross the target lesion, the subject will be included into ITT and mITT populations but excluded from PP population. That subject will be followed-up after discharge at 30-day, 6-month, 12-month and 24-month visits.
 
Analyses of all primary & secondary endpoints will be conducted in both the mITT and PP populations. The ITT population will serve as the primary set for safety assessments.

RATIONALE FOR NUMBER OF PATIENTS:	
With a total of 100 patients successfully treated by AURYON system in this study cohort, this study will serve as an unpowered pilot registry, towards a larger powered registry study that is planned to include approximately 1000 patients.

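### The screen-failure rule and the ITT definition conflict for a subject stopped on eligibility grounds after AURYON was attempted, and the plan does not say which prevails

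*Combined protocol and SAP*

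**What the plan says.** All the relevant text is in section 2, Protocol Summary, under Primary Analysis Plan, Analysis sets.

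- **ITT definition.** ITT consists of "all subjects who signed the informed consent form and underwent procedure with an attempt of using the AURYON system".
- **Screen-failure rule.** It begins "If a subject does not undergo complete procedure, either due to early or intraoperative non-eligibility of inclusion/exclusion criteria". The alternative trigger is missing evidence of stenosis of at least 50% "by fluoroscopy angiogram in the index procedure, the subject will be considered as a screen failure". The consequence is: "Screen failures will not be included into ITT population and will not be followed or part of the analysis".
- **Failed-attempt rule.** The next paragraph begins "If a subject undergoes an atherectomy attempt but the AURYON system could not be successfully used in any target lesion". It keeps that subject in ITT and out of mITT and PP, and adds: "That subject will not be followed-up after discharge".
- **Safety set.** "The ITT population will serve as the primary set for safety assessments".

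The primary safety endpoint in the same section is freedom from PPMAE up to discharge. In section 4, Table 1 schedules the recording of PPMAEs and other procedural complications at procedure, post-procedure and discharge. Footnote 2 to that table starts adverse-event capture at consent.

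**The concern.** The screen-failure rule turns on two things: the procedure was not completed, and the reason was eligibility or lack of significant disease. It expressly covers reasons found during the operation, but it does not say that it ceases to apply once AURYON has been attempted. The ITT definition turns on the attempt alone. For a subject with both an attempt and an eligibility-based stop, one rule includes and the other excludes.

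The sets are nested: PP lies within mITT, and mITT within ITT. A subject removed from ITT therefore appears in no analysis. The primary safety endpoint is made up of procedural events, so by the time such a stop is classified its outcome may already be known. Without a stated precedence, an exclusion that depends on the outcome is possible. That matters in a pilot whose stated product is point estimates for a larger registry.

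**Working it through.** The plan gives no sample size calculation, expected event rate or expected number of screen failures, so there is no figure to reproduce. The check has two parts.

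**1. The rules applied to each situation**

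| Situation | ITT definition | Screen-failure rule | Failed-attempt rule | Result |
|---|---|---|---|---|
| Ineligibility or stenosis below 50% found before any attempt | Out | Out | Not reached | Consistent: out |
| Attempted; stopped for technical failure or a complication, with no target lesion successfully treated | In | Not triggered (reason is not eligibility) | In | Consistent: in |
| Attempted; procedure incomplete; stop attributed to eligibility or to lack of 50% disease | In | Out | In if no target lesion was successfully treated; otherwise silent | **Conflict** |

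Only the third row is unresolved. Two terms that could have settled it, an attempt and a complete procedure, are not defined, and no order of precedence is given.

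**2. Size, as an illustration**

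Inputs: about 100 subjects (section 2, planned enrollment). The remaining inputs are assumptions: *e* = 0, 2 or 5 subjects with a PPMAE among 100 retained, and *k* = 1, 2, 3 or 5 further subjects who had a PPMAE and were removed as screen failures.

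Reported PPMAE-free rate = (100 − *e*)/100. 
Rate with the removed subjects restored = (100 − *e*)/(100 + *k*).

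| *e* | Reported | *k* = 1 | *k* = 2 | *k* = 3 | *k* = 5 |
|---|---|---|---|---|---|
| 0 | 100.0% | 100/101 = 99.0% | 98.0% | 97.1% | 100/105 = 95.2% |
| 2 | 98.0% | 98/101 = 97.0% | 96.1% | 95.1% | 98/105 = 93.3% |
| 5 | 95.0% | 95/101 = 94.1% | 93.1% | 92.2% | 95/105 = 90.5% |

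One event-bearing subject moves the estimate by about 1 point (0.9 to 1.0). Five move it by 4.5 points (95.0 − 90.5) to 4.8 points (100.0 − 95.2).

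A removed subject without an event hardly matters: with *e* = 5, restoring one gives 96/101 = 95.0%, unchanged to one decimal. The bias comes only from removed subjects who had an event.

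For scale, the exact (Clopper-Pearson) 95% interval for 95/100 is 88.7% to 98.4%; with three event-bearing subjects restored, 95/103 has an interval of 85.3% to 96.6%.

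**The case against.** The strongest reply is that the three paragraphs can be read as a sequence: ineligible or without significant disease, so a screen failure; attempted but not successfully used, so ITT only; used but not fully crossed, so ITT and mITT. Read that way, an intraoperative finding means one made on the table before any attempt. Most eligibility criteria are knowable before the case. A target lesion in a bypass, or stenosis below 50%, would normally be seen on angiography before the device is used. This reading agrees with the ITT definition and is probably what was meant, but it is not written, and the literal rule says otherwise.

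The reply does dispose of some stronger readings:

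- A reader might infer that complications of aborted procedures in general can vanish from the safety set. They cannot under these rules. Failed attempts are expressly kept in ITT, and a complication is not an eligibility criterion.
- A reader might infer that exclusion criterion 2, "Planned use of another atherectomy device in the same procedure", can be triggered mid-case when AURYON fails and the operator turns to another device. This strains the word planned, which naturally describes an intention held before the case. Where no target lesion was successfully treated, the failed-attempt rule also keeps that subject in ITT.
- A reader might infer that events concentrate in incomplete procedures, or that the operator decides who is a screen failure. The documents state neither.
- A reader might see loss of post-discharge follow-up as peculiar to screen failures. ITT-only subjects are not followed after discharge either, and the primary safety endpoint ends at discharge.

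It is also fair to say that no hypothesis test or decision threshold is affected, that the assumed shifts from one to three subjects are small beside the sampling error, and that Table 1 already provides for recording the events. The last point does not close the gap, because a recorded event in a screen failure is still barred from the analysis.

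**Conclusion.** The concern holds for a limited group: consented subjects in whom AURYON was attempted and the procedure was then stopped for an eligibility reason or for lack of 50% disease. For them the plan contains two contrary rules about membership of the primary safety set, which is more than a missing detail. Any PPMAE in such a subject could be left out, at about 1 percentage point per event-bearing subject in about 100. That size rests on the assumed event counts above. The documents do not give the number of such subjects, and it may be zero.

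Severity is moderate. The study is descriptive and unpowered, and the likely intent is benign. But this error runs in one direction, since omitting a subject with an event can only make the safety rate look better.

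**What to change.** Amend the analysis-set text in section 2 as follows:

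1. Limit screen failure to subjects with no AURYON attempt, and define an attempt as introduction of the AURYON catheter.
2. State that every consented subject with an attempt stays in ITT, whatever the reason for stopping, with PPMAEs counted to discharge. Membership of mITT and PP then follows from their existing definitions.
3. Treat eligibility violations discovered after the attempt as protocol deviations.
4. Report the number of screen failures, the reason for each, and any adverse events recorded in them after consent.

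The cost is about one clause and one short descriptive table. Table 1 already schedules PPMAE recording to discharge, so no new assessment is needed. The downside is a few more subjects in the safety denominator and possibly a slightly less favourable safety rate.

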	
System in a post-market (commercial device use) setting will be enrolled and will be followed for 24 months post index procedure.
 
Enrolled subjects will undergo endovascular PAD treatment that includes atherectomy using the AURYON system, according to institutional standard of care. Data collection will include prospective data collection and medical record review of procedures performed according to standard of care, at the study protocol specific follow up time-points.

OBJECTIVES:	To evaluate the safety and efficacy of AURYON Atherectomy System in the treatment of de novo, re-stenotic and ISR lesions in infra-inguinal arteries of Peripheral Artery Diseases (PAD) subjects, in a real-world setting. This is a pilot registry study towards a subsequent large pivotal registry (PATHFINDER II).
ENDPOINTS:	
Primary Endpoints:
 
 1. Primary Efficacy: Acute Procedural Success Percentage of subjects with successful revascularization of target vessel defined as $\leq 30\%$ residual stenosis at the index lesion post atherectomy using the AURYON system and final adjunctive treatment (if required), as evaluated by angiographic corelab. 2. Primary Safety: Percentage of subjects with freedom from peri-procedural major adverse events (PPMAE), defined as (a) flow-limiting dissection, (b) clinically significant distal embolization, (c) bailout stenting, (d) major/unplanned amputation, (e) target vessel perforation requiring endovascular or surgical repair or (f) death, till discharge. 
Secondary endpoint(s):
 
 1. Rate of device related complications requiring intervention, defined as peri procedural MAEs, reported by the operating physician as caused directly due to the use of the AURYON device. 2. Rates of post-discharge MAEs over time; defined as: (a) Unplanned target limb amputation, (b) cardiovascular death, (c) clinically driven target lesion revascularization¹, (d) target vessel revascularization (TVR). 3. Patency rate, defined as (1) $< 50\%$ stenosis at the treated lesion, with peak systolic velocity ratio (PSVR) of < 2.5, as

[figure not shown]
¹ Clinically-Driven Target Lesion Revascularization (CD-TLR), defined as a reintervention performed for $\geq 50\%$ diameter stenosis (confirmed by angiography) within 5 mm of the target lesion after documentation of recurrent clinical symptoms of PAD following the index procedure.

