3 STUDY SCHEMA

4 SCHEDULE OF ACTIVITIES

Table 1. Schedule of Events for Screening and Enrollment, AURYON atherectomy Procedure and Post-Procedure Follow-up

Study assessment	Pre-Procedure	Procedure	Post-procedure	Hospital discharge	30 Days (±1 weeks)	6, 12, 24 Months (±1 Month)
Medical history & demographics	X					
Physical Examination	X					X
Informed Consent	X					
Angiographic evaluation of target lesion	X	X	X			
PAD Intervention including AURYON Atherectomy		X				
Quantitative DUS						X
ABI ⁰	X					X
Rutherford Classification	X					X
WIQ	X					X
Record of relevant medications ¹	X	X		X	X ³	X ⁴
Record of PPMAEs ² and other procedural complication		X	X	X		
Record of MAEs ²					X ³	X ⁴

⁰ Toe-brachial index (TBI) will be taken for subjects with non-compressible vessels

¹ Relevant medications: anticoagulant and anti-platelets.

² Adverse events should only be captured after signing of the Informed Consent Form.

³ The visits may be done via phone call for record of any reportable adverse events and relevant medications.

⁴ In case that subject is not showing up to one or more of these follow-up visits, the site should contact the subjects by telephone to collect as much data as possible of any reportable adverse events and relevant medications.

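### Subjects with a failed AURYON attempt belong to the primary safety set but are not followed after discharge, so a complete post-discharge ITT MAE rate cannot be obtained

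*Combined protocol and SAP*

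**What the plan says.** All references are to the combined protocol and SAP.

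- **ITT definition** (Section 2, Primary Analysis Plan): consented subjects who "underwent procedure with an attempt of using the AURYON system". The mITT population narrows this to subjects in whom at least one lesion was actually treated with the device.
- **Failed attempts** (same row): where the system could not be used in any target lesion, "the subject will be included into ITT population but excluded from mITT and PP populations". The next sentence reads "That subject will not be followed-up after discharge".
- **Incomplete crossing** (same row): subjects who were treated but whose lesion was not fully crossed stay in mITT and are seen at 30 days and 6, 12 and 24 months.
- **Analysis sets** (same row): "Analyses of all primary & secondary endpoints will be conducted in both the mITT and PP populations", followed by "The ITT population will serve as the primary set for safety assessments". The second sentence carries no time limit.
- **Endpoints** (Section 2): the primary safety composite closes with "e) target vessel perforation requiring endovascular or surgical repair or (f) death, till discharge". Secondary endpoint 2 is "Rates of post-discharge MAEs over time; defined as: (a) Unplanned target limb amputation, (b) cardiovascular death", plus clinically driven target lesion revascularization and target vessel revascularization.
- **Follow-up of the cohort** (Section 2): Study Description gives 24 months for enrolled subjects. Study Duration gives two years for all of them.
- **Contact mode** (Section 4, Table 1): footnote 3, attached to the 30-day column, says "The visits may be done via phone call for record of any reportable adverse events and relevant medications". Footnote 4, attached to 6, 12 and 24 months, brings in the telephone only when a subject misses a visit.

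**The concern.** Post-discharge MAEs (amputation, cardiovascular death, repeat revascularization) are safety outcomes, and the plan names ITT as the primary safety set. By definition, the subjects in ITT but not in mITT are the failed attempts, and they are the ones whose data collection stops at discharge. After that point ITT holds no information that mITT does not.

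This is not ordinary loss to follow-up. It is built into the design and triggered by device failure, so it cannot be presumed unrelated to outcome. The peri-procedural composite counts dissection, distal embolization and perforation, so the plan itself recognises that an attempt can injure the vessel. Such an event is recorded if it shows itself before discharge. A later consequence, or an event first apparent at home, is not. Nor does the plan say how these subjects would enter a post-discharge ITT summary if one were produced.

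**Working it through.** The plan states no event rate, failure rate or power calculation, so there is no figure to reproduce. The check has two parts.

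**1. Endpoint window against follow-up**

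| Outcome | Window | Failed attempts observed? | Complete in ITT? |
|---|---|---|---|
| PPMAE (primary safety) | to discharge | yes | yes |
| Post-discharge MAE (secondary 2) | discharge to 24 months | no | no |

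The gap is confined to the second line.

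**2. Possible size**

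Inputs:
- 100 treated subjects, from the rationale for the number of patients. That row counts subjects successfully treated, so failures are taken as additional.
- *k* failed attempts: assumed 1, 5 or 10.
- 24-month MAE proportion: assumed 15% in treated subjects (m = 15) and 40% after a failed attempt.

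Formulas:
- ITT under the assumed rates = (15 + 0.40*k*) / (100 + *k*)
- Lower bound, no failed-attempt subject has an MAE = 15 / (100 + *k*)
- Upper bound, all of them do = (15 + *k*) / (100 + *k*)

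| *k* | mITT | ITT, assumed rates | Bounds on ITT |
|---|---|---|---|
| 1 | 15% | 15.4/101 = 15.2% | 14.9-15.8% |
| 5 | 15% | 17/105 = 16.2% | 14.3-19.0% |
| 10 | 15% | 19/110 = 17.3% | 13.6-22.7% |

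The width of the bounds is *k*/(100 + *k*), whatever the treated rate: 4.8 points at *k* = 5 and 9.1 at *k* = 10. With 20/100 in mITT, for example, they are 19.0-23.8% and 18.2-27.3%.

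If failures instead fell within a total of 100, the ITT rates would be (95 × 0.15 + 5 × 0.40)/100 = 16.25% and (90 × 0.15 + 10 × 0.40)/100 = 17.5%, nearly the same.

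For scale, the exact 95% CI for 15/100 is about 8.6-23.5%. The assumed-rate shifts of 1.2 and 2.3 points lie well inside it.

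**Will the case arise?** The chance of at least one failure in 100 attempts is 1 - (1 - *f*)^100. For assumed failure rates *f* of 1%, 2% and 5% this gives 63%, 87% and 99%.

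**The case against.** The best defence is that the plan can be read coherently. ITT serves safety up to discharge, where the primary safety endpoint ends and every ITT subject is observed. Post-discharge MAEs are a secondary endpoint, and the plan assigns all secondary endpoints to mITT and PP, whose members are followed. Study Description speaks of subjects treated with the system, so its 24 months need not cover a failed attempt. The registry is a descriptive, unpowered pilot, and a few failures would move the rate by less than its sampling error.

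Much of this stands, and it rules out several stronger readings that a reader might infer:

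- *That the primary safety result is compromised.* It is not, because its window closes at discharge.
- *That there can be no post-discharge ITT result at all.* All other ITT subjects are followed, so a censored or bounded ITT estimate is possible. Only a complete one is not.
- *That the subjects with the worst prognosis are lost.* The documents say nothing about prognosis after a failed attempt. Higher risk is plausible but assumed.
- *That failed attempts would be counted as event-free.* Nothing in the plan says so, and the proper comparator is the planned mITT result.
- *That Table 1 already provides telephone follow-up at every visit.* It does so routinely only at 30 days.

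What the defence does not answer is that the sentence naming ITT for safety has no time limit, that Study Duration makes no exception, and that late harm after a failed attempt is unrecorded on either reading.

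**Conclusion.** The point holds in a limited form. As written, a complete post-discharge ITT MAE rate cannot be obtained, the missing data are determined by device failure, and the no-follow-up rule conflicts with the two years of follow-up stated for all subjects. The primary safety endpoint is sound, and mITT and PP results after discharge will exist.

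The numerical effect is probably modest: 1.2 points with 5 failures and 2.3 with 10, on assumed MAE rates of 15% and 40%. Without any assumption about prognosis, the bounds span 4.8 and 9.1 points. The number of failures is itself assumed throughout. The case for change rests less on bias in the pilot estimate than on two facts: delayed harm after an attempt would go unseen, and closing the gap is cheap.

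**What to change.** **Preferred.** Remove the no-follow-up rule as far as MAE collection is concerned. For failed-attempt subjects, record MAEs and relevant medications by telephone or chart review at 30 days and 6, 12 and 24 months, with no DUS and no clinic visit. This means extending the telephone mode in Table 1 footnotes 3 and 4 to these subjects as their routine contact. Report post-discharge MAEs in ITT alongside mITT and PP, with the number of failed attempts and the reasons for them.

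**If follow-up is not extended.** State that ITT safety covers only the period to discharge, name mITT as the post-discharge safety set, and report the number of and reasons for failed attempts. Reconcile the Study Description, Study Duration and Primary Analysis Plan rows accordingly.

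**Cost.** The preferred change needs a small amendment and about four contacts per failed-attempt subject: some 20 contacts for 5 such subjects (4 × 5) and 40 for 10 (4 × 10). Medical record review is already a data source in the Study Description. The alternative costs only wording, but leaves late harm after a failed attempt unrecorded.

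### Acute procedural success is planned only in mITT and PP, so attempts in which AURYON could not be used leave the denominator and success per attempt is overstated whenever they occur

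*Combined protocol and SAP*

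**What the plan says.** Section 2 (Protocol Summary), under Primary Analysis Plan, defines three nested sets:

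- ITT: "all subjects who signed the informed consent form and underwent procedure with an attempt of using the AURYON system".
- mITT: "all ITT subjects who underwent atherectomy using the AURYON system for at least one lesion".
- PP: "all mITT subjects for whom the AURYON catheter fully crossed at least one target lesion".

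The same section says what happens to two kinds of incomplete device use. Where an attempt was made but AURYON could not be used in any target lesion, "the subject will be included into ITT population but excluded from mITT and PP populations". Where AURYON was used but did not fully cross the lesion, "the subject will be included into ITT and mITT populations but excluded from PP population".

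It then allocates the endpoints: "Analyses of all primary & secondary endpoints will be conducted in both the mITT and PP populations". The next sentence reads "The ITT population will serve as the primary set for safety assessments". No ITT analysis of efficacy is planned, and neither mITT nor PP is named as the lead.

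Under Endpoints, acute procedural success is the percentage of subjects with core-lab residual stenosis of 30% or less at the index lesion after AURYON atherectomy and any final adjunctive treatment. No explicit rule says how to score a subject who had an attempt but no AURYON atherectomy.

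**The concern.** Entry to either efficacy set depends on something observed after the attempt began: whether the device could be used (mITT), and whether it also crossed (PP). For a success endpoint, selecting on device performance removes from the denominator people who bear on the question. The result is success given that AURYON could be used, whereas the stated objective is efficacy in a real-world setting, where an attempt may fail.

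The estimates are the product of this pilot. The Primary Analysis Plan says they will supply point estimates for the large-scale registry, which the Rationale for Number of Patients puts at about 1000 patients. A rate conditional on device use, carried forward as if it were a rate per attempt, would set expectations too high. None of the planned efficacy analyses would show the gap.

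**Working it through.** The plan has no sample size, power or alpha calculation to reproduce. The check is denominator arithmetic.

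**Inputs**
- M = subjects in mITT. Set to 100 for illustration, in line with the 100 successfully treated patients in the Rationale for Number of Patients.
- s = successes in mITT. Assumed to be 95; the documents give no expected rate.
- F = attempts in which AURYON could not be used in any target lesion (in ITT, not in mITT). The documents give no count, so a range is shown.
- Scoring: the F subjects are non-successes, because the endpoint requires AURYON atherectomy.

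**Formulas**
- mITT rate = s/M
- ITT rate = s/(M+F)
- Overstatement = s/M − s/(M+F) = (s/M) × F/(M+F)

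**Results for s/M = 95/100 = 95.0% (exact 95% CI 88.7 to 98.4)**

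| F | ITT rate | Overstatement in mITT |
|---|---|---|
| 0 | 95/100 = 95.0% | 0 |
| 2 | 95/102 = 93.1% | 0.95 × 2/102 = 1.9 points |
| 5 | 95/105 = 90.5% (83.2 to 95.3) | 0.95 × 5/105 = 4.5 points |
| 10 | 95/110 = 86.4% (78.5 to 92.2) | 0.95 × 10/110 = 8.6 points |

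At F=10 the ITT rate lies below the lower limit of the mITT interval (88.7%), so the interval reported for mITT would not convey the difference.

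**Sensitivity to the assumed rate.** At 80/100 in mITT the gap is 3.8 points for F=5 and 7.3 for F=10. At 98/100 it is 4.7 and 8.9. The size depends mainly on F.

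**PP.** Suppose 95/100 succeed in PP, 5 further subjects are not crossed and do not succeed, and 5 more are device-unusable. Then PP = 95/100 = 95.0%, mITT = 95/105 = 90.5% and ITT = 95/110 = 86.4%. The extra PP gap requires that uncrossed subjects succeed less often than crossed ones. That is plausible but not certain, since adjunctive treatment counts towards the endpoint.

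**Opposite scoring.** If the device-unusable subjects were treated by other means and all counted as successes, F=5 would give (95+5)/105 = 95.2%, slightly above mITT. The endpoint wording does not support that scoring.

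**The case against.** The endpoint describes the result after AURYON atherectomy, which is the mITT population, so the set and the endpoint can be said to match. No sentence in the plan says that a subject without AURYON atherectomy counts as a failure. Some attempts may also end for reasons other than the device, since the Device Description requires a guidewire that crosses the lesion intraluminally. The study is an unpowered descriptive pilot with no hypothesis, margin or success threshold, and ITT is defined, so a reader given the counts by set could rebuild the per-attempt rate.

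Much of this stands. No test or decision rule is harmed, scoring as non-success follows from the endpoint wording rather than from a stated rule, and the gap is zero if no such subject occurs. But the plan writes a specific rule for these subjects, so it foresees them. It does not commit to reporting the counts alongside the success rate. Success conditional on device use is a legitimate supportive quantity; it does not answer the real-world objective.

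**Conclusion.** The point holds. As written, the plan overstates acute procedural success per attempt in mITT whenever at least one AURYON attempt ends without the device being usable, provided that some mITT subjects succeed. At an assumed 95% mITT rate in 100 subjects, the overstatement is about 2 points at F=2, 4.5 at F=5 and 8.6 at F=10. These sizes rest on assumed counts and on scoring the excluded subjects as non-success.

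A reader might infer more than the documents support:

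- *That both sets discard all AURYON failures.* mITT keeps uncrossed lesions and every treated subject with residual stenosis above 30%. It drops only attempts with no usable target lesion.
- *That the inflation is certain and could reach 14 points.* Take 100 attempts with 10 unusable and 10 uncrossed, 97% success in PP and half of the uncrossed succeeding. Successes are 0.97 × 80 + 5 = 82.6, so PP minus ITT is 97.0 − 82.6 = 14.4 points. That is the PP contrast at failure counts for which the documents give no basis. On the same inputs mITT is 82.6/90 = 91.8%, a gap of 9.2 points.
- *That the safety set is contradictory.* The allocation sentence does place all primary endpoints in mITT and PP, but the next sentence names ITT as primary for safety. Read together, mITT and PP are additional for safety.

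**What to change.** Amend the endpoint-allocation sentence in section 2, Primary Analysis Plan, so that:

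1. Acute procedural success is reported in ITT as the lead estimate.
2. Subjects in whom AURYON could not be used in any target lesion are scored as non-success, by an explicit rule.
3. mITT and PP are kept as supportive analyses.
4. The number of attempts excluded from each set is reported with the rates.

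The safety set needs no change beyond the existing statement that ITT is primary.

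The cost is wording. These subjects are already in ITT, and Table 1 (section 4) schedules procedural and post-procedural angiography and recording of peri-procedural events to discharge. Scoring them as non-success needs no additional core-lab reading. The site cap and the target of 100 are worded around successfully treated subjects; it would help to say which set they count, but the ITT rate can be calculated either way. The downside is a somewhat less favourable reported rate. The change should be made before results are seen.
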